Specific Aim #1: To determine if progesterone +TNP is superior to placebo +TNP for prolonged and 7-day point prevalence of smoking abstinence rates at the end of 8 weeks of treatment and at 1 and 3 month follow-up time points. We will also evaluate the safety and tolerability of progesterone treatment, compared to placebo. Our co-primary outcome measures will be 7-day point prevalence of smoking abstinence and breath CO at the end of treatment and 1- and 3-months after the end of the trial.

Specific Aim #2: To determine if progesterone + TNP treatment, compared to placebo + TNP, improves response inhibitory function, as assessed by the Stroop, The Go/No Go task, and the Digit Symbol Task.

Specific Aim # 3: To determine if progesterone + TNP treatment, compared to placebo + TNP, leads to a greater reduction in cigarette craving and nicotine withdrawal symptoms, as assessed

by the Questionnaire on Smoking Urges-Brief (QSU-B) and the Minnesota Nicotine Withdrawal Scale (MNWS), respectively.

Specific Aim #4: To evaluate with affective changes, as shown on the Positive and Negative Affect Schedule, mediates the effects of progesterone on smoking abstinence.

Exploratory Aim: We will evaluate the degree to which serum estradiol and progesterone levels achieved during the trial are associated with a) greater smoking abstinence, b) improved response inhibition, and c) less craving and withdrawal symptoms.

2. **Background:** Describe the background information that led to the plan for this project. Provide references to support the expectation of obtaining useful scientific data.

Nicotine addiction continues to be the main preventable cause of death in developed countries, with an estimated 435,000 premature deaths in the U.S and 5 million deaths worldwide (11). About 18% of women and 22% of men in the US smoke (11). Some evidence suggests that women respond less favorably to NRTs, even though they maintain their nicotine addiction with lower levels of nicotine intake than men (12-15). Women, compared to men, may be more vulnerable to the complications of smoking, most notably lung cancer (16, 17). In the US, lung cancer kills more women than the breast and colon cancer combined. These findings support the need to develop more effective treatments tailored for female smokers.

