#### *Overview of the study design*

This will be a double-blind, placebo-controlled, pilot, randomized clinical trial. A total of 50 women who have regular menstrual cycles will be randomized to either progesterone (200 mgs BID) + Transdermal Nicotine Patch (TNP; 21 or 14 mg/day) or placebo + TNP (21 mg or 14mg/day) for 8 weeks. TNP will be tapered after 4-6 weeks as recommended by the Clinical Practice Guidelines for treating tobacco dependence (9). Participants who smoke more than 10 cigarettes per day will receive the following dose of TNP: 21mg/24 hours for 4 weeks, 14mg for weeks 5 and 6 and 7 mg for weeks 7 and 8. Participants who smoke between 5-10 cigarettes per day will receive the following dose of TNP: 14mg/24 hours for 6 weeks, 7mg for weeks 7 and 8.

Study medications will be discontinued at the end of Week 8. All participants will also be provided behavioral treatment for smoking cessation. Participants will be inducted onto progesterone (or placebo) + TNP over a one-week period (Week 1) during the mid luteal phase, within a week before menses and the target quit date will be set for the 5 (+/-2) days after onset of menses. Participants will have post-trial follow-up visits at 1 and 3 months following the end of the trial. The main study outcomes will be self-report of smoking abstinence, biochemically verified smoking abstinence, measures of cigarette craving and nicotine withdrawal, and measures of response inhibition.

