#### *Human subjects*

**Recruitment:** Recruitment will take place over 1.5 years, requiring enrollment of approximately 2-3 subjects per month. In our previous studies, we have been able to recruit on average 4 female smokers per month. Recruitment is further explained in Human Subjects but will be accomplished by direct screening in our reproductive health centers (20% of women seen for services in these centers are smokers), direct mail invitations, posters and flyers placed in local obstetrician-gynecologist offices. We have successfully used these techniques to recruit substance users, smokers and women with premenstrual dysphoric disorder in prior clinical trials. [name] has a secondary appointment in Obstetrics & Gynecology and has conducted numerous studies that entailed screening women in the reproductive health settings of Yale New Haven Hospital and their faculty (see Biosketch).

Update June 2017: All participants had blood levels of progesterone drawn. We were blind to assignment of participants but at the end of the study found that those who were randomized to active progesterone had low progesterone levels. This could be due to the progesterone preparation or the fact that smokers metabolize it very quickly. In any case, the low progesterone levels in the active treatment group obviates our ability to test our hypothesis that progesterone augmentation assists abstinence for smokers. Given the lack of funds, we cannot repeat the project. Rather, we are recruiting a second cohort and are using a commercially available oral micronized progesterone rather than the previous medication that was compounded for the study. We plan to enroll a minimum of 12 people with an imbalanced ratio of 6 active to 1 placebo. We will continue to obtain plasma levels of progesterone. This will enhance our ability to test our hypothesis. If need be in a final analysis, and give that this is a pilot project, we may be able to use the participants randomized to placebo in the first cohort and second cohort and the participants randomized to active in the second cohort.

Update September 2017: We request an additional blood draw (timeline is around Visit #6 or #7 to confirm progesterone plasma levels and compliance with pill taking. The second blood draw will be the same as the first one, completed at a professional lab on the first floor of the research site building. Approximately 6 ccs of blood will be drawn for each.

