Determination of Eligibility and Baseline Visit: This interview will occur between estimated days 18-24 of the typical menstrual cycle. This will be a 120 minute visit. It will be broken down into two parts: 1) we will determine eligibility for the randomized clinical trial (RCT) and 2) we will obtain baseline measures for those who are eligible. The first procedure will be obtaining informed consent (please see consent procedures below). In the process of consent, we will explain to the provisionally eligible participant that part of the visit will be to determine eligibility for the RCT. For determination of eligibility, women will complete the NIDA Quickscreen (10); DSM 5 psychosis screener and DSM 5 screener for major depressive disorder, panic disorder or post-traumatic stress disorder (PTSD; current). Any positive responses on these measures will trigger an evaluation, including the SCID and assessment by a study clinician (a physician for medical issues; a psychologist, physician or social worker if the issues is an exclusionary psychiatric diagnosis) that will indicate whether or not the participant is eligible; 2) a medical history will be gathered to obtain information on allergies, especially progesterone, use of medication, pregnancy planning, history of breast cancer, deep vein thrombosis, coagulation problems, liver failure, cervical intraepithelial neoplasm, allergy to nuts, etc; and 3) nicotine intake history including use of all nicotine products, number of cigarettes smoked and use of other nicotine products in the previous month, prior treatment for smoking cessation; prior intolerance or allergy to transdermal nicotine patch; 4) laboratory tests that include urine for pregnancy, cotinine and drugs of abuse and expired breath CO.

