The RA will complete a checklist that indicates eligibility criteria. The checklist will be reviewed by study clinician who will confirm that this information has been gathered and that the participant meets criteria for participation. For women who continue to be eligible, the RA and/or study clinician will ask baseline measures that include: 1) a menstrual history form including module for diagnosis of premenstrual dysphoric disorder and menstrual cycle dating, the Fagerstrom Test for Nicotine Dependence (FTND) (11); the Minnesotal Nicotine Withdrawal Scale (MNWS) (12), the Questionnaire on Smoking Urges-Brief (QSU-B) (13) and the Positive and Negative Affect Schedule(14) . They will also complete the following neurocognitive tasks: 1) the Stroop, (15) 2) Go/No Go, 3) Digit Symbol Substitution Test (part of the WAIS III), 4) The Shipley Institute of Living Scale (SILS) is a paper-and-pencil, self-administered scale that consists of a 40-item vocabulary and a 20-item pattern recognition section (16).

Randomization/Visit 1: After eligibility is confirmed and the baseline assessments are completed, women will be randomized. Women will then begin smoking cessation counseling and will receive two weeks supply of their study medication, TNP + either oral micronized progesterone or placebo. They will be instructed to apply one nicotine patch /day and to take one pill twice daily after the visit. They will be instructed to set a quit date for the 5 (+/-2) days after the onset of menses, ideally around the 3-4th day when perimenstrual symptoms have abated and before estrogen peaks. We will call them at the estimated time of menses onset to confirm dates and quit date plans. We used similar strategies in smoking studies and menstrual cycle studies (6).

Treatment Phase (Visit 2 to 8): Women will be seen for follow up around days 7-11 of their menstrual cycle, shortly after their quit date. This visit will confirm that treatment with TNP + progesterone or placebo was initiated and maintained for the estimated 2 weeks since Visit 1. Medication compliance will be assessed by pill count. Support and counseling will be

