provided for the quit attempt. Assessments will be repeated although the neurocognitive battery will only be done a second time at this first follow up visit. A blood draw will be completed twice throughout the study, the first around Visit #2 and the other around Visit #6 or Visit #7 at a professional lab on the first floor of the research site building. Approximately 6 ccs of blood will be drawn for each.

Other assessments will be conducted weekly for the additional weeks of the study. Assessments will include a weekly calendar of cigarettes smoked, if any, breath CO. We will collect urine for cotinine if the breath test is negative and there are concerns about compliance with TNP. If there is a possibility that a participant is pregnant (i.e. she is not menstruating or in the week following menstruation) we will also test urine for positive pregnancy. Additionally, subjects will have brief behavioral treatment sessions for smoking abstinence.

End of study (Visit 8), Termination and follow-up: At the end of the 8-week treatment period, participants will complete their weekly ratings, collect breath CO. Participants and study staff will be asked to guess their treatment condition (progesterone or placebo) and will discontinue study capsules and TNP. All participants will be encouraged to remain abstinent from smoking (9). Follow-up visits will be scheduled at 1 and 3 months after the end of the study. At follow up, assessments of smoking and the PANAS will be repeated. We will not repeat the neurocognitive measures.

Strategies to minimize attrition and enhance follow up: We will: 1) rapidly assign study treatments after application confirmation of eligibility, 2) thoroughly explain study treatments and requirements, and 3) specify uniform procedures across treatment conditions regarding study staff's handling of participants who miss or come late to sessions. Study investigators will monitor participants who drop out and explore with the staff reasons for the dropouts. We will follow the full randomized sample, regardless of their retention in treatment, by including: 1) a thorough explanation at the consent interview of the importance of follow-ups, 2) collecting at least three verified locators who are likely to have knowledge of a subject's whereabouts, 3) paying participants to cover transportation and parking for follow-up visits.

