pattern mixture models (26) and perform sensitivity analyses. In sensitivity analyses, participants who miss visits will be coded as smoking. Exploratory analysis will include plasma estradiol and progesterone levels as covariates in order to determine if they contribute to treatment response and PANAS scores as mediators of response to progesterone or placebo. Secondary analyses (the MNWS QSU-B) will be modelled similarly. The main outcome measures for the Stroop test are throughput and interference score. For the SST, the main outcomes are stop signal reaction time (msec) and go reaction time (msec). We will use hierarchical linear models with each cognitive measure as separate longitudinal outcomes and treatment group assignment as regressors.

**Power:** The sample size of 25 per condition was selected to provide an adequate assessment of feasibility and estimate effect sizes. Nonetheless, we determined what level of power we would have based upon a significance level of  $p < 0.05$ , 2 sided test for 7-day or prolonged abstinence. If rates of abstinence are 0.2 in the TNP only group and 0.4 in the progesterone and TNP group then the power would be 88%. If the rate of abstinence in the treated group is 0.38, power is reduced to 80%. In prior studies with the Stroop and SST, we found effect sizes  $> 0.5$  of progesterone vs placebo. Our sample size would have adequate power ( $> 80\%$ ) to detect a 2-fold difference in response. Clearly, these are large differences between groups but would provide a stable effect size estimate for a larger trial if findings are suggestive of a therapeutic effect of the combination treatment.

**Timeline:** We will use the first 3 months for study set up that will include final human subjects' approval, hiring and training of staff, database set up, computerization of the interview and assessment measures. Recruitment will begin immediately afterward. We will conduct ongoing data cleaning and will prepare reports for the human subjects' board, the DSMB and NCI at regular intervals. The final analysis and study report will occur in the last 3 months of the work period.

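### Progesterone levels measured after the quit date are to be related to abstinence with no time ordering, so quitting or pill-taking could drive the level and mimic a dose-response

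*Combined protocol and SAP*

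**What the plan says.** The Exploratory Aim in Section V.1 reads: "We will evaluate the degree to which serum estradiol and progesterone levels achieved during the trial are associated with a) greater smoking abstinence". It goes on to response inhibition, craving and withdrawal. Section V.12, Data Analysis, gives the method in one sentence: "Exploratory analysis will include plasma estradiol and progesterone levels as covariates in order to determine if they contribute to treatment response". No time ordering, restriction by arm, or adjustment for smoking or adherence is attached to it.

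Section V.3, Study Procedures, places the two blood draws: "the first around Visit #2 and the other around Visit #6 or Visit #7". On Visit 2 the same section says: "Women will be seen for follow up around days 7-11 of their menstrual cycle, shortly after their quit date". The overview states that the "target quit date will be set for the 5 (+/-2) days after onset of menses". The baseline visit lists "laboratory tests that include urine for pregnancy, cotinine and drugs of abuse and expired breath CO", with no hormone level, so no pre-quit level is available as an anchor.

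The June 2017 update (Section V.3, repeated in Section VI.A.2) reports low progesterone levels in the active group of the first cohort and comments: "This could be due to the progesterone preparation or the fact that smokers metabolize it very quickly". The September 2017 update requests the second draw, to confirm plasma levels and compliance with pill-taking.

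**The concern.** The analysis asks whether higher levels go with more abstinence. By the time blood is drawn, some women will have stopped smoking and others will not. If smoking speeds clearance of progesterone, women who are smoking at the draw will have lower levels because they are smoking. If women who relapse also take fewer capsules, the bias runs the same way. A positive association would then appear even if progesterone did nothing for abstinence.

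The result could carry weight. Low levels are the stated reason for changing the product and recruiting a second cohort, and the June 2017 update says continued level measurement will help test the hypothesis. A level-abstinence association could be read as evidence that progesterone works once exposure is adequate. As written, the analysis cannot separate that explanation from the reverse one.

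**Working it through.** The plan gives no figure for this analysis, so there is none to reproduce. The check has two parts.

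**Timing.**
- The quit date is 5 ± 2 days after onset of menses, so about days 3 to 7. Visit 2 is around cycle days 7 to 11. The first draw therefore falls about 0 to 8 days after quitting (7 − 7 to 11 − 3).
- The second draw was requested in September 2017, after the June 2017 update described the first cohort as finished. On those dates the first cohort (25 per arm planned) would have the Visit 2 level only, and the Visit 6 or 7 draw mainly concerns the second cohort.
- The second cohort has a minimum of 12 women at 6:1, so 12 × 6/7 ≈ 10 active.

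**Size with no drug effect, by simulation in the active arm.**

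Assumptions that are not in the documents:
- The SD of the log level between women is 0.8.
- Smoking at the draw lowers the level by r = 30%, 50% or 70%, a log shift d = −ln(1 − r) = 0.36, 0.69 or 1.20.
- Concurrent case: 30% are abstinent at the draw.
- Lagged case: 40% are abstinent at the draw; later abstinence is 70% in those women and 10% in the others.

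The test compares mean log level by abstinence, t = (m1 − m0) / [s√(1/k1 + 1/k0)]. It counts only significant results in the direction of higher level with more abstinence, nominally 2.5%.

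| Comparison | Active women | r = 30% | r = 50% | r = 70% |
|---|---|---|---|---|
| Level and abstinence at the same time | 25 | 14% | 46% | 89% |
| Same | 10 | 9% | 21% | 49% |
| Visit 2 level against later abstinence | 25 | 9% | 21% | 45% |
| Same | 10 | 6% | 10% | 20% |

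A repeat run agreed to within about two percentage points, and with r = 0 the rate was about 2% to 2.5%.

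Hand check, concurrent, 25 women, r = 50%: the expected groups are 7.5 and 17.5, so √(1/7.5 + 1/17.5) = 0.436. The expected t is (0.69/0.8)/0.436 ≈ 1.98, against a critical value of 2.07 on 23 df. That gives a chance of about 47%.

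Why lagging reduces the bias without removing it: later abstinence is 0.4 × 0.7 + 0.6 × 0.1 = 0.34. Of the later-abstinent women, 0.28/0.34 = 82% were abstinent at the draw. Of the others, 0.12/0.66 = 18% were. The log-level difference between the later groups is therefore (0.82 − 0.18) × d = 0.64d, not zero.

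**Effect of the remedy.** Adding one term for smoking status at the draw to the lagged comparison returns the one-directional rate to about 2% to 3%.

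**Sensitivity to the SD.** In the lagged case with 25 women and a two-fold effect, a two-sided 5% test rejects in 42% of runs at SD 0.5 and 22% at SD 0.8. A larger SD lowers it further. Section V.3 gives a half-life of 3 to 4 hours with twice-daily dosing and states no draw time relative to dose. If draw time is random over the dosing interval, the 46% (concurrent) falls to about 33%, and the lagged figure to about 17%.

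**The case against.** Several points on the other side stand.

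- The protocol's remark on metabolism is one of two guesses and refers to smokers as a group. It does not say that levels rise on quitting or fall on relapse, nor how fast. A reader might infer that the protocol concedes reverse causation. It concedes only that the mechanism is possible.
- A reader might apply the Visit 6 or 7 argument, that the level explains abstinence already won or lost, to all 25 planned active women. The dates do not support that. For the first cohort the lagged Visit 2 figures are the more relevant ones.
- A reader might infer that the trial's treatment estimate is distorted. Aim 1 has its own GEE model, and nothing in Section V.12 takes the treatment effect from the exploratory model. In a two-arm model containing the level (25 per arm, no true effect, smoking halves the active-arm level), the arm coefficient does shift by about −0.16 on the risk scale. That needs active levels 2 log units above placebo (e² ≈ 7-fold). The shift is only about −0.06 at 1 unit and about 0 at 0.5. The low active-arm levels reported in June 2017 make the large separation doubtful for the first cohort.
- The analysis is labelled exploratory, the aim is worded as association, and the 1- and 3-month outcomes come after both draws.
- Heavy adjustment is not workable. With about 10 active women and, say, 3 abstinent, a model with level, breath CO, cigarettes and pill count has four predictors for three events. Adjusting for pill count also removes real variation in exposure.

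These points limit the scope and shape the remedy. They do not supply the missing time ordering.

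**Conclusion.** The concern holds for the exploratory level-abstinence analysis. As written, it cannot distinguish an effect of level on quitting from an effect of quitting or pill-taking on level. If smoking lowers the level by 30% to 70% and the log-level SD is 0.8, the chance of a spurious positive finding is about 9% to 45% for the Visit 2 level against later abstinence with 25 active women, and 6% to 20% with 10. Concurrent comparison raises this to 14% to 89% and 9% to 49%. The nominal rate is 2.5%. The size of the smoking effect, the SD and the persistence of smoking status are all assumptions, so the bias is possible and could be material, but it is not demonstrated. The primary randomised comparison is untouched.

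**What to change.** Replace the covariate sentence in Section V.12, Data Analysis, with a specification along these lines:

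1. The level-response analysis is run within the active arm.
2. The Visit 2 level is used only to predict abstinence at later visits. The Visit 6 or 7 level is used to describe exposure and compliance, or only for the 1- and 3-month outcomes. For those, point prevalence is the cleaner choice, because prolonged abstinence counts back to before that draw.
3. A sensitivity analysis adds a single term for smoking status at the draw, from breath CO or the weekly cigarette calendar, with a note that this may also remove a genuine early effect. Pill count is reported descriptively.
4. The randomised treatment estimate is taken only from the model without hormone levels.
5. Any association is reported as non-causal.

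The data are already planned for collection, so the cost is wording. The price is fewer data points in an exploratory analysis and a more cautious conclusion from it.

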Main outcomes are prolonged smoking abstinence (Y/N at each point) and rates of 7-day point prevalence of abstinence(Y/N at each point). Following the recommendations of the Society for Research on Nicotine and Tobacco workgroup, the 7-day point prevalence is defined by self-reported smoking abstinence for the last 7 days, and expired carbon monoxide <10 ppm. Prolonged smoking abstinence is self-reported smoking abstinence starting with a 2-week grace period after the quit day (i.e., last 5 weeks of the treatment phase) without relapse to: the end of the trial, 1 month and 3 months post trial. Relapse is defined by a) smoked for 7 consecutive days or b) smoked at least once each week for 2 consecutive weeks, or c) missed 2 consecutive weekly appointments or 2) failed breath test at any previous outcome assessment. Additional outcomes include measures of withdrawal (MNWS and QSU-B), and response inhibition (Stroop and SST).

Data Analysis: We will follow CONSORT guidelines for the conduct and reporting of the trial. Descriptive statistics will be used to summarize the data on all randomized subjects, although, as per CONSORT, these parameters will not be included in the statistical model for primary analyses. Aim #1: To determine whether progesterone with TNP is superior to placebo and TNP we will use generalized estimating equations (GEE), an autoregressive correlation structure a binomial distribution and either identity or log link. A time-by-treatment interaction will be included in the GEE model. The 8-week period will include a continuous version for the time variable and the follow up periods will treat time as categorical. A GEE model such as this can evaluate whether there is an overall difference between the progesterone and the placebo groups and whether the rate of change in smoking abstinence is different between the two groups. For data that are missing, we will perform inverse weighting to determine if data are missing at random (25). The weight will be the inverse of the probability not dropping out. If there are concerns of informative dropout and/or informative intermittent missing data, which is typical of clinical trial data, we will use

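### Craving and withdrawal scores (Aim 3) borrow a model built for yes/no abstinence, with no named contrast and no role for the baseline score

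*Combined protocol and SAP*

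**What the plan says.** Specific Aim #3 (Section V, item 1) asks whether progesterone plus patch "leads to a greater reduction in cigarette craving and nicotine withdrawal symptoms", measured by QSU-B and MNWS. Both are taken at the baseline visit, before randomization; the list in Section V, item 3, Study Procedures includes "the Questionnaire on Smoking Urges-Brief (QSU-B) (13) and the Positive and Negative Affect Schedule".

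In Section V, item 12, Data Analysis, the whole analysis of these scales is "Secondary analyses (the MNWS QSU-B) will be modelled similarly". The model referred to is the Aim 1 GEE for abstinence, with "an autoregressive correlation structure a binomial distribution and either identity or log link". On time: "The 8-week period will include a continuous version for the time variable and the follow up periods will treat time as categorical". Also: "A time-by-treatment interaction will be included in the GEE model". The plan says this model can assess "whether there is an overall difference between the progesterone and the placebo groups" and also whether the rate of change differs. Of the descriptive summaries it says "these parameters will not be included in the statistical model for primary analyses". The cognitive scores, by contrast, are given hierarchical linear models of their own.

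**The concern.** Three things are left open.

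- **Outcome family.** MNWS and QSU-B yield scale scores. A binomial model cannot be carried over to them unchanged, and no alternative is named.
- **Contrast.** Two are on offer and neither is assigned to Aim 3. Because the aim is worded as a reduction, an analyst could reasonably take the rate of change as the test. Baseline is measured while the women still smoke, and Visit 2 comes shortly after the quit date, so the later slope need not reflect how much relief the drug gave.
- **Baseline score.** Aim 3 is a question about change, yet the plan does not say whether baseline enters as a covariate, as a week-0 outcome, or not at all.

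At stake is whether Aim 3 yields an interpretable effect estimate. The Power paragraph gives estimating effect sizes as a purpose of the sample size.

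**Working it through.** The plan states no SD, effect size or power for MNWS or QSU-B, so there is no figure to reproduce.

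**Inputs from the documents.** 25 per arm (Power). First follow-up about two weeks after Visit 1, then weekly, which I take as weeks 2 to 8, seven post-quit visits (Study Procedures). I assume both scales are rated at each of these visits; the weekly list does not name them.

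**Assumptions.** Score SD 1, no dropout, and the effect curves below. Differences are progesterone minus placebo, so negative means benefit.

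**1. What each contrast shows.** For a difference curve d(t), the straight-line treatment-by-time slope under equal weights is Σ(t − t̄)d(t) / Σ(t − t̄)². For weeks 2 to 8, t̄ = 5 and the denominator is 28. With baseline added as week 0, where d = 0, t̄ = 35/8 = 4.375 and the denominator is 49.875.

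| Assumed effect | Slope, weeks 2-8 (SD/week) | Slope, week 0 included (SD/week) | Average, weeks 2-8 (SD) |
|---|---|---|---|
| Constant −0.5 | 0/28 = 0 | −2.188/49.875 = −0.044 | −0.50 |
| −0.5 at week 2, fading to 0 at week 8 | 2.333/28 = +0.083 | 1.240/49.875 = +0.025 | −0.25 |
| −0.5 at week 2, fading to −0.25 | 1.167/28 = +0.042 | −0.474/49.875 = −0.0095 | −0.375 |
| Growing, −0.1 per week | −0.100 | −0.100 | −0.50 |

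Autoregressive weights, as the plan specifies, do not remove the pattern. With a benefit of 0.8 SD at week 2 that halves every 1, 2 or 4 weeks, and correlation 0, 0.5 or 0.8, the post-quit slopes run from about +0.09 to +0.13 SD/week while the averages are −0.23, −0.36 and −0.50 SD. With week 0 included, the slopes shrink to between −0.03 and +0.05.

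**2. What the baseline score is worth.** The variance of a woman's seven-visit mean is v, and its covariance with her baseline is c. The standard error of the group difference is √(2v/25) unadjusted and √(2(v − c²)/25) adjusted.

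- Equal correlation 0.6: v = (1 + 6 × 0.6)/7 = 0.657 and c = 0.6. Unadjusted SE = √(0.08 × 0.657) = 0.229. Adjusted SE = √(0.08 × (0.657 − 0.36)) = 0.154, or about 0.156 after multiplying by √(1 + 1/46) for estimating the baseline coefficient.
- Power for 0.5 SD, two-sided 0.05, noncentral t with 48 and 47 df: 57% unadjusted (0.5/0.229 = 2.18) and 88% adjusted (0.5/0.156 = 3.21). Simulation gave 56% and 88%.
- Visit 2 alone, from simulation: about 41% unadjusted and 57% adjusted.
- Correlation decaying as 0.8 per week: v = 0.641, and c = (0.8² + … + 0.8⁸)/7 = 0.361. Unadjusted SE = √(0.08 × 0.641) = 0.226. Adjusted SE = √(0.08 × (0.641 − 0.131)) = 0.202, about 0.204 with the same multiplier. The gain is then modest.

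**The case against.** Modelling scales similarly need not mean identically. The plan already mentions an identity link and uses linear models for the cognitive scores, so a sensible analyst would not fit a binomial to these totals. That is fair, but the plan should state the choice, and a clause would do it.

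The plan also names an overall difference, and on average that contrast keeps the right sign in every trajectory tried. A reader might infer that Aim 3 will come out with the wrong sign. The documents do not support that: nothing in them makes the slope the Aim 3 test, and they give no time course for craving, withdrawal or the drug effect. With baseline coded as week 0, the share of simulated trials with a wrong-signed slope was about 84% for an effect fading to zero, 35% for one fading by half and 4% for a constant effect. What stands is that the contrast is not designated. With continuous time and an interaction, the treatment coefficient is the fitted difference at time zero unless time is centred or the contrast is defined, so the overall difference needs a definition too.

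A reader might also infer that baseline scores are barred from Aim 3. The exclusion is stated for primary analyses and reaches Aim 3 only through the cross-reference. Omitting baseline as a covariate costs precision and leaves chance imbalance (SE √(2/25) = 0.28 SD); it does not cause a sign reversal.

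**Conclusion.** The concern holds as a specification gap in a secondary aim. The cross-reference supplies an outcome family that does not fit, two contrasts with neither chosen, and no role for baseline scores already collected. These three points need no assumed trajectory.

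The consequences do depend on assumptions. If the post-quit slope were used, it would miss a constant benefit and point the wrong way for an early, fading one. Baseline adjustment of the averaged difference cuts its standard error from about 0.23 to 0.16 SD under equal correlation 0.6, but only from about 0.23 to 0.20 under decaying correlation. The figure of 25 per arm is the original design. The June 2017 update allows second-cohort active women to be compared with placebo women from both cohorts. That comparison is not fully randomized, so baseline adjustment would then also bear on bias.

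This should be corrected before the Aim 3 data are analysed. It is not a threat to the trial as a whole.

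**What to change.** Replace the sentence on the secondary analyses with wording such as:

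> MNWS and QSU-B will each be analysed with a linear mixed model (or a Gaussian GEE) over Visits 2-8, with visit as a category, treatment, treatment-by-visit, and the woman's baseline score as covariate. The Aim 3 contrast is the baseline-adjusted mean difference averaged over Visits 2-8. Visit-specific differences, including Visit 2, will be reported as supportive. The slope difference is not the test of Aim 3.

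The sponsor should choose one of the two model types now. The average is preferable to Visit 2 as the sole contrast. A quit date 5 ± 2 days after menses onset and a visit on cycle days 7-11 put that rating roughly 0 (7 − 7) to 8 (11 − 3) days after quitting, and a Visit 2 test favours an assumed early peak.

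The cost is analysis-plan wording only. The baseline scores are already collected; the plan should also confirm that both scales are rated at each of Visits 2-8.
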